10 TRIAL ASSESSMENTS AND PROCEDURES

10.1 Endpoints

Primary endpoint:

Change from baseline of total hair density (No. of hairs per cm2) on the scalp after 12 weeks of treatment

Secondary endpoints are:

Change from baseline of total hair density (No. of hairs per cm2) on the scalp after 8 weeks of treatment

Change from baseline of hair growth parameters after 8 and 12 weeks of treatment:

- Cumulative hair thickness (mm/cm²)
- Hair thickness (µm/cm², mean median)
- Hair length (mm/cm²; mean, median)
- Terminal hair density (n/cm²)
- Vellus hair (<40µm thick) density (n/cm²)
- Total hair growth (µm/day/cm²)
- Hair growth (μ m/day/cm², mean median)
- TrichoScan Änagen/Telogen ratio
- Proportion of anagen hairs (%)
- Proportion of telogen hairs (%)
- Proportion of vellus hair (%)

To evaluate **the** safety based on:

- Any adverse events and adverse drug reactions reported
- Local tolerability assessments
- Vital signs and physical examination
- Abnormal safety laboratory parameters

10.2 Efficacy Assessments

10.2.1 Efficacy Variables

- Cumulative hair thickness (mm/cm²)
- Hair thickness (µm/cm², mean median)
- Hair length (mm/cm²; mean, median)
- Total hair density (n/cm²)
- Terminal hair density (n/cm²)
- Vellus hair (<40µm thick) density (n/cm²)
- Total hair growth (µm/day/cm²)
- Hair growth (µm/day/cm², mean median)
- Anagen hair density (n/cm²)
- Telogen hair density (n/cm²)

10.2.2 Methods for Efficacy Assessments: TrichoScan imaging and measurement

10.2.2.1 Determination of Clinical Response to Investigational Product

Photos of the treatment areas will be taken, and assessment of hair growth (hair count and hair density) calculated based on TrichoScan images. The analysis of the images will be performed centrally by a unit independent of the investigators. The analysis of the images will be performed while keeping the blind with regard to the treatment assignment. Assessment of hair growth will be performed as follows:

At Screening:

- 1. Treatment areas will be trimmed over a large area to achieve a hair length of 1mm;
- 2. Treatment areas (1.5 cm in diameter) will be selected and marked by a dot tattoo;

At visit 1 (day 1):

- 1. Selected treatment areas (1.5 cm in diameter) will be identified;
- 2. Selected treatment areas will be trimmed over a large area to achieve a hair length of 1mm;
- 3. A TrichoScan image is taken without hair dye with the TrichoScan camera/optics system held always in the same position;

At visit 2 (day 3):

- 1. Selected treatment areas (1.5 cm in diameter) will be identified;
- 2. A TrichoScan image is taken after hair dye with the TrichoScan camera/optics system held always in the same position **prior to IMP treatment**;

The procedures of visit 1 are repeated for visits 23 and 35. The procedures for visit 2 are repeated for visits 24 and 36.

For details of the TrichoScan imaging please refer to the TrichoScan manual.

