The trial period will consist of a screening period of up to 1 week followed by 12 weeks of dosing, three times per week. Each subject will receive two doses of the four trial treatment doses (0.00625, 0.025, 0.050, and $0.100 \mu g$ respectively) and the placebo dose. On each volunteer, two treatment areas will be selected on the head and the two selected doses will be allocated to the respective treatment areas according to the randomisation scheme. The treatment areas will be selected on the border between the bald surface and the surface with hair.

The subjects will be screened for eligibility at the screening visit where a physical examination and assessment of vital signs will be performed. Blood samples for safety and laboratory assessment will be taken. The subjects will return to the clinic for the inclusion visit (visit 1, day 1) 3 to 21 days later. If the subject is eligible for inclusion, the 2 treatment areas will be shaved and the centre of each treatment area where the trial treatments will be applied will be marked with a tattooed dot.

At visit 2, day 5, the first trial treatment application will be performed after TrichoScan imaging of the treatment areas. Subjects will then return to the clinic for treatment application three times per week with at least one day in between.

All subjects who have received at least one dose of trial drug will go through the procedures for safety and efficacy assessments at last visit (EOT, visit 38).

All adverse events will be followed until resolved or stabilised. Procedures for removal of subjects from therapy or assessments are described in Section 8.7.

Number of subjects:

A total of 60 healthy male subjects will be included.

Each subject will be treated at two sites. Each site will be treated with different treatments.

Thus, a total of 120 treatment areas will be available for treatment on the 60 subjects

Inclusion criteria:

The subjects must meet all of the following criteria to be eligible to enter the trial:

- 1. Healthy male, aged 18-55 years
- 2. Androgenetic alopecia (AGA)) Norwood/Hamilton grade 3V to 4/4a [1]
- 3. Caucasian, skin type I IV according to Fitzpatrick's classification [2]
- 4. Willing to have treatment areas shaved for TrichoScan® measurement marked with small semi-permanent dot tattoos
- 5. Willing and able to comply with scheduled visits
- 6. Willing to maintain the same hygiene products and skin cleansing habits during the trial period.

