Safety summaries will be performed on the safety analysis set. The Per-protocol set will be considered the primary efficacy subset of subjects. The Full analysis set will be used for a sensitivity analysis of the primary efficacy variable only.

1.1	Trial flow chart	

		Treatment period									
Visit number	Screening ^{a)}	1	2	3 - 21	22	23	24	25-36	37	38	EoT ⁱ⁾
Week	-3 to -1					1	- 12				
Day	-21 to -3	1	3	5 - 48	50	52	54	57 - 82	85	87	NA
Visit window (+/- days) with at least 1 day interval			1	1	1	1	1	1	1	1	1
Informed consent	X										
Physical examination ^{b)}	X	Х								Х	Х
Inclusion/exclusion criteria	X	Х									
Demographic data	X	X									
Medical and surgical history	X										
Vital signs °)	X	X								X	X
Concomitant medication	X	X	Χ	X	Х	X	X	X	X	X	X
Determ. of investing. Areas ^{d)}		Х									
Marking of test areas		Х									
Randomisation			Х								
Dot tattoo ^{e)}	X			X e)				X e)			
IP/ Placebo administration			X	х	Х		X	Х			
Shaving of treatment areas		Х				X				X	
TrichoScan		X f)	X			X f)	X		X f)	Х	
Safety assessment/ local tol.		X	Х	X	Х	X	X	X	X	X	Х
Blood sampling (haem. and clin chem) ^{g)}	X									X	X
Blood sampling (Hep B, Hep C, HIV)	X										
Urine sampling ^{h)}	X									X	X
Recording of AEs/SAEs		X	Χ	X	X	X	X	X	X	X	X

- a) The screening period is defined as the time between visit 0 and visit 1. The screening period will vary in length to accommodate flexibility in the planning of subject visit schedule.
- b) The physical examination will include: General appearance, mouth and throat, ears (left and right), lungs, abdomen, neurological
- c) Vital signs will include: Systolic and diastolic blood pressure (mmHg), heart rate (beats per minute), and body temperature
- d) The treatment areas will be evenly placed on the scalp
- e) The dot tattoo will be repeated if necessary during the course of the trial. Ensure that this performed at least 6 days prior to the next TrichoScan assessment.
- f) TrichoScan imaging will be performed without hair dye
- g) Haematology: haemoglobin, white blood cell count including differential cell count, red blood cell count, platelet count, coagulation (partial thromboplastin time and prothrombin time); Clinical Chemistry: Glucose, creatinine, total bilirubin, gamma-glutamyltransferase (GGT), alanine aminotransferase (ALAT), aspartate aminotransferase (ASAT), Electrolytes (Na, K), lactate dehydrogenase (LDH), C-reactive protein (CRP), total cholesterol

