7 INVESTIGATIONAL PLAN

7.1 Trial Design and Plan-Description

The trial is a multicentre, randomized, double-blind, placebo controlled phase 2 trial.

The trial centres will screen a sufficient number of subjects (approximately n = 90) to include 60 eligible male subjects. Subjects withdrawn for IMP-unrelated reasons will be replaced if treatment was performed for less than 4 weeks.

60 healthy male subjects, who are 18 to 55 years old and provide written informed consent will be included

The trial period will consist of a screening period of up to 3 weeks followed by 12 weeks of dosing. Each subject will receive their first doses at visit 2 (day 5). Subjects will then return to the clinic for treatment application 3 times per week with at least one day in between. 4 active dose strengths and one placebo dose will be used in the trial and each subject will be randomly assigned two of these 5 treatments. Thus, all 60 subjects will receive 2 doses.

The subjects will be screened for eligibility at the screening visit where a physical examination and assessment of vital signs will be performed. Blood samples for HIV/Hep-b/Hep-c, safety and laboratory assessment will be taken. The subjects will return to the clinic for the inclusion visit (visit 1, day 1) 3 to 21 days later. If the subject is eligible for inclusion, the 2 treatment areas will be shaved and the centre of each treatment area where the trial treatments will be applied will be marked with a tattooed dot.

At visit 2, day 3, the first TrichoScan imaging of dyed hair for determination of baseline total hair density per cm² and the first trial treatment application will be performed on the treatment areas. Subjects will then return to the clinic for treatment application three times per week with at least one day in between.

All subjects who have at least received one dose of trial drug will go through the procedures at the Follow up safety and efficacy assessments at the EoT visit.

All adverse events will be followed until resolved or stabilised. Procedures for removal of subjects from therapy or assessments are described in Section 8.7.

Trial Treatments

 $50 \ \mu$ I of the trial treatments will be applied intradermally at each treatment site in the centre marked with a tattooed dot. The dilutions and preparation of vials will be performed at the centre, by blinded personnel.

The trial treatments will consist of three times per week application of:

- FOL-005 0.00625 µg solution, or

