7.3 Discussion of Trial Design, Including the Choice of Control Groups

A randomised controlled blinded design is used. Such a design is most suitable to prevent and/or to minimize selection, performance, attrition, and detection bias.

The primary objective of this trial is to evaluate the effect of FOL-005 on scalp hair growth in healthy male subjects.

The TrichoScan is a reliable, well-validated phototrichogram method assessing the biological parameters of hair growth by combining dermoscopy with automatic digital image analysis for the measurement of human hair in situ. The TrichoScan system is designed to take reproducible images from shaved areas on the scalp. A good correlation between TrichoScan and manual evaluation of hair counts has been demonstrated [9, 10].

Safety and tolerability will be evaluated as secondary objectives. FOL-005 was considered safe and well tolerated in a previous phase 1 trial, FCS-001, as described in the investigator's brochure.

Each subject will have 2 treatment areas, A and B, evenly located on the scalp, at least 5 cm apart from each other. Treatment areas will be treated with either one of the following treatments: $0.00625 \,\mu g$, $0.025 \,\mu g$, $0.050 \,\mu g$, $0.100 \,\mu g$ and placebo according to the randomisation schedule.

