10.5.2 Experimental phase

Visit 1

- Re-check of the inclusion and exclusion criteria (see section 8.2 and 8.4);
- Physical examination (see section 10.4.3);
- Vital signs (see section 10.4.4);
- Documentation of demographic data;
- Update of previous and concomitant medication;
- Recording of AEs/SAEs;
- Identification of treatment areas;
- Marking of test areas;
- Shaving of test areas;
- TrichoScan imaging without hair dye;
- Safety assessment and local tolerance assessment (see section 10.4);

Visit 2

- Update of previous and concomitant medication;
- Recording of AEs/SAEs (record potential AEs also 15 min after first application);
- Safety assessment and local tolerance assessment (see section 10.4);
- Randomisation
- Identification of selected treatment areas;
- Marking of selected treatment areas;
- TrichoScan imaging including hair dye
- IP application

Visit 3 - 21

- Update of previous and concomitant medication;
- Recording of AEs/SAEs;
- Safety assessment and local tolerance assessment (see section 10.4);
- Optinal: repeat of tattooing, if necessary;
- Identification of selected treatment areas;
- IP application

Visit 22

- Update of previous and concomitant medication;
- Recording of AEs/SAEs;
- Safety assessment and local tolerance assessment (see section 10.4);
- Identification of selected treatment areas;
- IP application

Visit 23

- Update of previous and concomitant medication;
- Recording of AEs/SAEs;
- Safety assessment and local tolerance assessment (see section 10.4);
- Identification of selected treatment areas;
- Marking of selected treatment areas;
- Shaving ot test areas
- TrichoScan Image without hair dye

Visit 24

- Update of previous and concomitant medication;
- Recording of AEs/SAEs;
- Safety assessment and local tolerance assessment (see section 10.4);
- Identification of selected treatment areas;
- Marking of selected treatment areas;
- TrichoScan imaging including hair dye
- IP application

Visit 25 - 36

- Update of previous and concomitant medication;
- Recording of AEs/SAEs;
- Safety assessment and local tolerance assessment (see section 10.4);
- Optinal: repeat of tattooing, if necessary;
- Identification of selected treatment areas;
- IP application

Visit 37

- Update of previous and concomitant medication;
- Recording of AEs/SAEs;

- Safety assessment and local tolerance assessment (see section 10.4);
- Identification of selected treatment areas
- Shaving ot test areas;
- TrichoScan imaging without hair dye;

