Visit 38

- Update of previous and concomitant medication;
- Physical examination (see section 10.4.3);
- Vital signs (see section 10.4.4);
- Recording of AEs/SAEs;
- Safety assessment and local tolerance assessment (see section 10.4);
- Blood and urine sampling for assessment of safety laboratory parameters;
- TrichoScan imaging including hair dye

EoT visit (if not identical with Visit 38 due to early discontinuation)

- Update of previous and concomitant medication;
- Physical examination (see section 10.4.3);
- Vital signs (see section 10.4.4);
- Recording of AEs/SAEs;
- Safety assessment and local tolerance assessment (see section 10.4);
- Blood and urine sampling for assessment of safety laboratory parameters;

Subjects should refer to the clinical site three times a week at an interval of at least 1 day.

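### The week-12 image that yields the primary endpoint is assigned to two different visit pairs, with two different shaving visits and two dates for the baseline image

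*Combined protocol and SAP*

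**What the plan says.** **Imaging visits.** Section 10.2.2.1 describes how the efficacy images are obtained. Its visit 1 procedures are a trim to 1 mm followed by an undyed image; its visit 2 procedure is a dyed image before the injection. For the later time points it states: "The procedures of visit 1 are repeated for visits 23 and 35. The procedures for visit 2 are repeated for visits 24 and 36". The flow chart, printed in section 1.1 and again as Table 1 in 7.2.1, has injections but no TrichoScan in the column for visits 25 to 36. It marks the undyed image at visit 37 and the dyed image at visit 38. Section 10.5.2 agrees with the chart on imaging: it lists none for visits 25 to 36, an undyed image at visit 37, and "TrichoScan imaging including hair dye" at visit 38.

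**Shaving.** In both copies of the chart the row "Shaving of treatment areas" is marked at visits 1, 23 and 38, and visit 37 is blank. Section 10.5.2 lists "Shaving ot test areas" (spelling as printed) at visit 37 and no shaving at visit 38.

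**Day of the baseline dyed image.** The synopsis says "At visit 2, day 5, the first trial treatment application will be performed after TrichoScan imaging of the treatment areas". Section 7.1 gives both dates. One paragraph has "Each subject will receive their first doses at visit 2 (day 5" and a later one has "At visit 2, day 3, the first TrichoScan imaging of dyed hair for determination of baseline total hair density". The flow chart and 10.2.2.1 also use day 3.

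The week-8 pair, visits 23 and 24, is the same in all three places.

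**The concern.** Section 7.1 says the dyed image determines baseline total hair density, so the visit of the dyed image fixes the primary endpoint at both ends. A site that follows 10.2.2.1 takes the week-12 image earlier than one that follows 10.5.2, and before the last planned injection. A site that follows the shaving row of the flow chart takes its visit 37 image on areas last shaved at visit 23. Yet section 7.3 states: "The TrichoScan system is designed to take reproducible images from shaved areas on the scalp". Section 9.8.1 prohibits other shaving of the areas, so nothing in between would make up for the missing shave.

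Two features of the plan raise the stakes. First, the primary test (12.1.5, 12.3.3) is of change from baseline against zero within a dose level. A difference in imaging conditions between baseline and week 12 that is shared by all areas goes straight into that change and is not removed by a placebo comparison. The change to be detected is 13.6 hairs/cm², or 8% of 170 (12.2). Second, the trial is multicentre, and 13.5.2 counts any departure from protocol procedures as a deviation. Whichever section a site follows, it departs from another. Deviations are graded major or minor case by case, and major ones remove subjects from the per-protocol set, which is the primary efficacy set (12.1.1).

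**Working it through.** **Visit days.** The flow chart prints days 1, 3, 5–48, 50, 52, 54, 57–82, 85 and 87 for visits 1, 2, 3–21, 22, 23, 24, 25–36, 37 and 38. A grid of three visits per week, on days 1, 3 and 5 of each week, is

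day(v) = 7 × floor((v − 1)/3) + 1, 3 or 5.

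It reproduces every printed day except visit 21, where it gives 47 against a printed 48. That is within the ±1-day window. It puts visit 35 on day 80 and visit 36 on day 82.

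**Week 12 side by side**

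| | 10.2.2.1 | 10.5.2 | Flow chart |
|---|---|---|---|
| Shave or trim | visit 35, day 80 | visit 37, day 85 | visit 38, day 87 |
| Undyed image | visit 35, day 80 | visit 37, day 85 | visit 37, day 85 |
| Dyed image | visit 36, day 82 | visit 38, day 87 | visit 38, day 87 |

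**Gap between the two dyed-image dates.** 87 − 82 = 5 days. With windows of ±1 day, visit 36 spans days 81–83 and visit 38 spans days 86–88. The smallest gap is 86 − 83 = 3 days and the largest is 88 − 81 = 7 days. The windows never overlap.

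**Time from first injection to dyed image.** With visit 2 on day 3: 82 − 3 = 79 days (11.3 weeks) against 87 − 3 = 84 days (12.0 weeks). With visit 2 on day 5 and later visits on their printed days: 82 − 5 = 77 days (11.0 weeks) against 87 − 5 = 82 days (11.7 weeks). The second pair is conditional and does not fit the chart, because visit 3 already starts on day 5.

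**Injections given before the dyed image.** The chart's injection visits are 2–22 (21 visits) and 24–36 (13 visits), so 21 + 13 = 34. All 34 precede an image at visit 38. An image at visit 36, taken before that day's injection, follows 33. It follows 32 if visit 35 carries no injection, as visits 1 and 23 carry none.

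**Nominal interval from shave to image**

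- Baseline, dyed: 3 − 1 = 2 days, or 5 − 1 = 4 days if visit 2 is day 5.
- Week 8, dyed: 54 − 52 = 2 days.
- Week 12, dyed, under 10.2.2.1: 82 − 80 = 2 days.
- Week 12, dyed, under 10.5.2: 87 − 85 = 2 days.
- Week 12, dyed, under the flow chart: 0 days if the visit 38 shave comes before the image, or 87 − 52 = 35 days if it comes after.
- Week 12, undyed at visit 37, under the flow chart: 85 − 52 = 33 days since the visit 23 shave.

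These intervals are nominal. The visit windows also act on them: visit 37 on day 84 and visit 38 on day 88 would be 4 days apart.

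**Same visit numbers elsewhere.** Sections 10.4.3, 10.4.4 and 10.4.5 name visit 36 for the physical examination, vital signs and laboratory samples that the chart puts at visit 38. The numbering mismatch is therefore not confined to imaging.

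**The case against.** The best reply is that the documents nearly settle the imaging visit themselves. Only 10.2.2.1 names visits 35 and 36. The flow chart and 10.5.2 agree on 37 and 38, the synopsis puts the efficacy assessment at visit 38, and section 7.1 caps participation at 87 days, which is the day of visit 38. Counted from day 3, visit 38 is exactly 12.0 weeks. This suggests a cross-reference that was not updated. The shaving mark looks like an X one column out: the chart pairs shaving with the undyed image at visits 1 and 23, and 10.2.2.1 and 10.5.2 both do so at week 12. The second copy of the chart is a reprint, not independent confirmation. The known timing difference is 5 days in 84 and one or two injections in 34. A timing error falls on both areas of a subject at the same visit, so it would not by itself bias a comparison of dose with placebo.

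Much of this stands. Section 10.2.2.1 is the outlier on imaging, the 5-day shift alone may be modest, and the 33- and 35-day intervals come from the most literal reading of one cell.

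It does not remove the problem. Section 7.2.1 sends the reader to 10.2 for efficacy detail, so the outlier is the section a site would consult. The chart that supports visit 38 is also the one with the conflicting shave. And the planned primary test is against zero, not against placebo, so the comparison that would be protected is not the one specified.

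**Conclusion.** The concern holds. Current text gives two visit pairs for the week-12 images, two visits for the week-12 shave, and two days for the baseline dyed image. The competing dyed-image dates are 5 days apart (3 to 7 with windows), at 11.3 and 12.0 weeks from a day-3 first injection. The shave-to-dyed-image interval is a nominal 2 days under either 10.2.2.1 or 10.5.2, and 0 or 35 days under a literal reading of the chart.

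The day counts for visits 35 and 36 rest on the three-per-week grid, which matches the chart's printed days to within a day. The effect on hair density, in size or direction, cannot be computed from the documents. Any effect on the growth-rate and anagen/telogen endpoints is an assumption, because imaging details are left to a TrichoScan manual that is not included. The point still needs correction before the first subject is imaged: it concerns how the primary endpoint is acquired, and images taken at the wrong time or after the wrong preparation cannot be retaken.

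**What to change.** Reconcile section 1.1, Table 1 in 7.2.1, 10.2.2.1 and 10.5.2 so that one visit pair is named for week 12. The shave and undyed image should come at the first visit of the pair and the dyed image at the next, with the same shave-to-image interval as at baseline and week 8. State that interval explicitly with its own tolerance, since the general ±1-day windows let it drift.

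In the same edit, give visit 2 one day throughout the synopsis, 7.1, the flow chart and 10.2.2.1. Align the visit 36 references in 10.4.3 to 10.4.5 with the flow chart's visit 38.

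The cost is protocol wording and a flow-chart correction. No visit or procedure is added.
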